6.3 Description of analysis sets

Two analysis sets are specified for efficacy, the full analysis set and the per-protocol analysis set. The primary efficacy variable of change from baseline in HbA1c will be reanalyzed using the per-protocol analysis set if more than 10% of the subjects in any regimen are found to significantly violate the terms and conditions of the protocol. Otherwise, efficacy analysis will be restricted to the full analysis set. These analysis sets and the safety analysis set are described as follows.

6.3.1 Full analysis set

The full analysis set will include all randomized subjects (as randomized) who received at least one dose of study medication during the 24-week double-blind treatment period, who have a non-missing baseline value and at least one post-baseline efficacy value for at least one efficacy variable during the 24-week double-blind treatment period. The intention-to-treat principle will be preserved despite the exclusion of subjects who took no study medication, as the decision of whether or not to begin treatment during the randomized treatment period could not be influenced by knowledge of the assigned treatment. Missing values will be replaced by the last observation carried forward (LOCF) approach.

6.3.2 Per protocol analysis set

The per-protocol analysis set is a subset of the full analysis set consisting of subjects who do not violate the terms of the protocol which may affect the primary efficacy endpoint significantly. All decisions to exclude subjects from the primary data set will be made prior to the unblinding of the study.

6.3.3 Safety analysis set

Safety analysis will be based on the safety analysis set which consists of all randomized subjects who received at least one dose of study medication.

6.4 Method of statistical analysis

6.4.1 Analysis of primary and secondary efficacy for the 24-week treatment period

The primary and secondary efficacy analyses will be based on the full analysis set. The primary endpoint may also be analyzed with the per-protocol analysis set. Treatment effects will be determined through pair-wise treatment group comparisons: each dapagliflozin treatment group versus placebo. No statistical comparisons will be made amongst the dapagliflozin groups.

For endpoints not examining insulin dose, the last post-baseline measurement prior to the first up-titration will be used for subjects whose insulin dose is up-titrated (i.e., patients are censored at the time of up-titration). Endpoints examining insulin dose will also use LOC, but without censoring at the time of titration. To directly assess the relationship between changes in insulin dose and HbA1c, changes in HbA1c will also be summarized using the observations from the same time points as analyzed for insulin dose as a supportive analysis.

The change from baseline to week 24 in HbA1c will be analyzed using an analysis of covariance model (ANCOVA) with factors for treatment group and use of other OADs as fixed effects, and covariate for baseline HbA1c. The model will be used to derive least squares estimates of the treatment differences (each dapagliflozin dose group versus placebo) in mean change with corresponding p-value and two-sided 95% confidence interval. Further, two-sided 95% confidence intervals for the mean change within each treatment group will be calculated.

To preserve the Type I error rate ≤ 0.050 (two-sided) across the primary and within each dose group for the four key secondary endpoints, a hierarchical step-wise procedure will be used to interpret the statistical significance of these treatment comparisons. The details of the step-wise procedure are provided in Section 6.2.

Continuous secondary efficacy variables will be analyzed by means of an ANCOVA for change from baseline using treatment group and use of other OADs as fixed effects and baseline value as a covariate. By analogy to the primary efficacy variable, the model will be used to derive point estimates and two-sided 95% confidence intervals for the mean change within each treatment group as well as for the difference in mean change between the dapagliflozin and placebo groups. Nominal p-values for the difference between the treatment groups will be provided.

When examining secondary endpoints defined within a subgroup (e.g., change in HbA1c in subjects with baseline HbA1c $\geq 9\%$, change in HbA1c in subjects with baseline HbA1c $\geq 7.5\%$ and $< 9\%$, change in HbA1c in subjects with baseline BMI ≥ 27 kg/m², change in HbA1c in subjects with baseline BMI ≥ 30 kg/m², absolute change in body weight in subjects with baseline BMI ≥ 27 kg/m², absolute change in body weight in subjects with baseline BMI ≥ 30 kg/m², absolute change in seated systolic BP and seated diastolic BP in subjects with baseline seated systolic BP > 140 mmHg), the same methods will be used.

Treatment effects on the primary endpoint will also be summarized within different subgroups to examine the robustness of the results across various categories of baseline characteristics. The two strata (with OADs and without OADs) will be considered subgroups. For this particular subgroup analysis, the interaction term between treatment and strata will be added to the ANCOVA model and tested for significance. Additionally, 95% confidence intervals of the treatment differences between each dapagliflozin group and placebo within each stratum will be provided. Other subgroups and their analyses will be outlined in the SAP.

The time course of all continuous variables will be presented using standard descriptive summary statistics calculated at each scheduled measuring time point and the last individual measuring time point. Moreover, standard descriptive summary statistics will be calculated for the absolute change from baseline to each scheduled measuring time point after baseline and the last individual measuring time point.

Discrete variables will be summarized by counts, proportions, and corresponding 95% confidence intervals. Comparisons between the treatment groups will be analyzed using two-sided Fisher's exact tests.

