- if at least 3 fasting SMBG diary measurements from the past 7 days exceed 220 mg/dl (12.2 mmol/l). Diary fasting SMBG values that meet these criteria should be recorded in the eCRF.

The last HbA1c and FPG values measured by central laboratory prior to the up-titration of insulin dose will be carried forward for the efficacy analyses at week 24 (visit 9).

Reduction of daily insulin dose shall be ordered by the investigator under the following circumstances:

Within the first 7 days of active randomized treatment:

- if the patient reports two or more readings of plasma glucose value ≤ 80 mg/dl (≤ 4.4 mmol/l).

After the first 7 days of active randomized treatment:

- if the patient reports two or more readings of plasma glucose value ≤ 70 mg/dl (≤ 3.8 mmol/l).

Patients should be encouraged to contact the investigator in such a case to allow the reduction of insulin dose.

Background OAD therapy may only be decreased if a concern of hypoglycaemia arises in a patient that has already been completely taken off of insulin.

Background OAD therapy may not be increased at any time during the study

Patients will be discontinued from the study if they have had complete withdrawal of both insulin and if applicable other OAD, they subsequently experience more than one event of major hypoglycaemia, and the investigator decides that current treatment puts the patient at risk of either repeated hypoglycaemic events or major hypoglycaemia. Major hypoglycaemia is defined as a symptomatic event requiring external assistance due to severe impairment in consciousness or behaviour with a capillary or plasma glucose value < 3 mmol/l (< 54 mg/dl) and prompt recovery after glucose or glucagon administration.

Randomized patients who discontinue early should complete the procedures described for visit 18 (end of treatment period) immediately following discontinuation of study drug. Thereafter patients should return for the 3 week follow up visit so that visit 19 procedures can be completed.

Long-term, double-blind extension period I (Visits 10–12, Weeks 25-48)

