The patients will stop taking investigational product at the end of treatment visit 18 (Week 104).

Follow-up period (Visit 19, Week 105-107)

Patients will stop taking the investigational products at Visit 18 (end of treatment period) and thereafter be followed for 3 weeks. During this time patients can be treated as appropriate without any restrictions by the protocol.

Table 1 Study plan

	Enrol- ment	24-week double-blind treatment period							24-week double-blind extension period I				56-week double-blind extension period II						Follow up
Visit number	1	2	3	4	5	6	7	8	9	10	11	12	13	14	15	16	17	18	19
Study week	-2	0	1	4	8	12	16	20	24	32	40	48	49	52	65	78	91	104	107
Informed consent	x											x ^h							
Demography and Medical history		x																	
Inclusion/exclusion criteria	x ^e	x ^c										x ^j							
Randomization		x																	
Brief Physical examination			x	x	x	x	x	x		x	x			x	x		x		x
Complete Physical Examination		x							x			x				x		x	
Vital signs		x	x	x	x	x	x	x	x	x	x	x		x	x	x	x	x	x
Orthostatic BP measurement		x	x	x		x			x		x	x		x		x		x	x
Weight		x	x	x	x	x	x	x	x	x	x	x		x	x	x	x	x	x
Height		x																	
BMI		x	x	x	x	x	x	x	x	x	x	x		x	x	x	x	x	x
Waist circumference		x							x			x				x		x	
12-lead ECG		x							x			x				x		x	
Concomitant medication	x	x	x	x	x	x	x	x	x	x	x	x	x ⁱ	x	x	x	x	x	x

Table 1 Study plan

	Enrol- ment	24-week double-blind treatment period								24-week double-blind extension period I				56-week double-blind extension period II						Follow up
Visit number	1	2	3	4	5	6	7	8	9	10	11	12	13	14	15	16	17	18	19	
Study week	-2	0	1	4	8	12	16	20	24	32	40	48	49	52	65	78	91	104	107	
Laboratory assessments	x	x	x	x	x	x	x	x	x	x	x	x		x	x	x	x	x	x	
Pregnancy testa	x	x	x	x	x	x	x	x	x	x	x	x		x	x	x	x	x	x	
Collection of Pharmacokinetic blood samples ^g					x				x											
Local FPG (HemoCue)		x	x	x	x	x	x	x	x	x	x	x		x	x	x	x	x	x	
AEs		x	x	x	x	x	x	x	x	x	x	x	x ⁱ	x	x	x	x	x	x ^f	
Serious adverse events	x	x	x	x	x	x	x	x	x	x	x	x	x ⁱ	x	x	x	x	x	x ^f	
Dispense investigational product		x		x	x	x	x	x	x	x	x	x		x	x	x	x			
Drug accountability of investigational product				x	x	x	x	x	x	x	x	x		x	x	x	x	x		
Diet / life-style advice	x	x	x	x	x	x	x	x	x	x	x	x	x ⁱ	x	x	x	x	x	x	
Dispense of glucometer and/or supplies/ provide instruction	x	x	x	x	x	x	x	x	x	x	x	x		x	x	x	x	x		
Dispense patient diary	x	x	x	x	x	x	x	x	x	x	x	x		x	x	x	x	x		

Table 1 Study plan

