Baseline is defined as the assessment performed at the randomization visit (Visit 2). The laboratory parameters that will be measured to assess efficacy are displayed in [Table 5](#) by visit. The results from baseline and onwards will not be reported to the investigator unless the values meet the defined insulin titration criteria see section [3.4.2](#) except for total cholesterol, HDL-C, LDL-C, TG and FFA which will be reported.

Table 5 Efficacy laboratory variables for Enrolment, 24-Week Double-Blind Treatment Period and 80-Week long term Double-Blind Extension Period I and II

Visit	1	2	3	4	5	6	7	8	9	10	11	12	13	14	15	16	17	18	19
Study Week	-2	0	1	4	8	12	16	20	24	32	40	48	49	52	65	78	91	104	107
HbA1C	x	x	x	x	x	x	x	x	x	x	x	x		x	x	x	x	x	x
FPG		x	x	x	x	x	x	x	x	x	x	x		x	x	x	x	x	x
Total cholesterol		x							x			x				x		x	x
LDL-C		x							x			x				x		x	x
HDL-C		x							x			x				x		x	x
TG		x							x			x				x		x	x
FFA		x							x			x				x		x	x

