If a patient experiences an unexpected hypoglycemic event in spite of high FPG or HbA1c levels, the investigator should consider a change in timing of the insulin dose and/or a change of the insulin regimen, rather than considering uptitration of the insulin dose.

The last HbA1c and FPG values measured by central laboratory prior to the increase in insulin dose will be carried forward for the efficacy analyses at week 24 (visit 9).

Reduction of daily insulin dose will not be allowed except for reasons of patient safety under the following circumstances:

Reduction of insulin dose shall be ordered by the investigator if the patient reports two of more readings of plasma glucose value ≤ 70 mg/dl (≤ 3.8 mmol/l). In addition, the investigator may consider an insulin dose adjustment (dose reduction or change in timing of insulin dose) in patients who report symptoms suggestive of hypoglycaemia without confirmatory glucose measurements if, in the opinion of the investigator, the patient is at increased risk of further hypoglycemic episodes without such insulin dose adjustments.

Diary fasting SMBG values that meet these criteria should be recorded in the eCRF.

Hypoglycaemic events

The patient will be asked to always self-monitor fasting plasma glucose in case of symptoms suggestive of hypoglycaemia and to register any signs of hypoglycaemia in the supplied diary.

- A hypoglycaemic event can be either
- An episode with symptoms and confirmed low glucose.
- An episode with low glucose.
- An episode with symptoms suggestive of hypoglycaemia when glucose was not measured.

For the evaluation of hypoglycaemic events special attention will be given to hypoglycaemia as defined in accordance with CPMP guidance on clinical investigation of medicinal products in the treatment of diabetes mellitus, as described below.

- Major hypoglycaemic events, defined as symptomatic events requiring external assistance due to severe impairment in consciousness or behaviour, with a capillary or plasma glucose value < 54 mg/dL (< 3.0 mmol/L), and prompt recovery after glucose or glucagon administration.

- Minor hypoglycaemic event, defined as either a symptomatic event with a capillary or plasma glucose value <63 mg/dL (<3.5 mmol/L), and no need for external assistance, or an asymptomatic blood glucose measurement <63 mg/dL (<3.5 mmol/L).
- Events suggestive for hypoglycaemia, with symptoms that the patient experiences as hypoglycaemia and no confirmative measurement.

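### Censoring at first up-titration (Protocol 6.4.1) leaves patients up-titrated before Visit 9 with no usable lipid, FFA or waist value, because these six variables are measured only at weeks 0 and 24

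*Protocol*

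**What the plan says.** Protocol 6.4.1 divides the efficacy endpoints into two groups. Those examining insulin dose are analysed without a cut at titration. For all the others the rule is: "For endpoints not examining insulin dose, the last post-baseline measurement prior to the first up-titration will be used". The section adds in parentheses that "patients are censored at the time of up-titration". Lipids, FFA, waist, blood pressure and body weight all fall in the second group.

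Sections 3.1 and 4.7.4.1 describe the carry-forward with reference to two variables. Section 3.1, on the 24-week period, says: "The last HbA1c and FPG values measured by central laboratory prior to the up-titration of insulin dose will be carried forward for the efficacy analyses". Section 4.7.4.1 says: "The last HbA1c and FPG values measured by central laboratory prior to the increase in insulin dose will be carried forward". Neither mentions any other variable, and neither says that the rule is confined to these two.

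The visit schedule is in two tables. Table 5 in section 4.6, headed "Efficacy laboratory variables for Enrolment, 24-Week Double-Blind Treatment Period and 80-Week long term Double-Blind Extension Period I and II", places the five lipid and FFA measurements at Visits 2, 9, 12, 16, 18 and 19. The row "Waist circumference" in Table 1 (section 3.1) is marked at Visits 2, 9, 12, 16 and 18. Neither has an entry between week 0 and week 24.

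For missing values, section 6.3.1 provides last observation carried forward and nothing else. It admits a patient to the full analysis set on one post-baseline value of any efficacy variable. Section 6.4.2 reuses the 24-week methods, in general, for weeks 48 and 104.

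**The concern.** A rule that takes the last value before up-titration needs at least one post-baseline value before up-titration. HbA1c, FPG, weight and blood pressure are measured at every site visit and normally supply one. The six variables above cannot supply one if up-titration comes before Visit 9. The rule then has nothing to carry forward, and it also bars the week-24 measurement that the schedule does provide.

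At stake is what the week-24 lipid and waist comparisons estimate. Up-titration is a response to hyperglycaemia after randomisation, so removing these patients selects on a post-randomisation outcome that treatment is expected to influence. The randomised comparison is replaced by one among patients who did not need more insulin, and the share removed can differ between arms.

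The result is also odd in practice. A patient who stops study drug early without up-titration completes the Visit 18 procedures, which include lipids and waist, and contributes a value. A patient who stays on study drug to week 24 and gives the sample contributes nothing if insulin was raised earlier.

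**Working it through.** **1. Does a usable value exist?**

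| Variable | Measurements in weeks 0–24 | Post-baseline values before an up-titration that precedes Visit 9 |
|---|---|---|
| TC, LDL-C, HDL-C, TG, FFA (Table 5) | weeks 0, 24 | 0 |
| Waist (Table 1) | weeks 0, 24 | 0 |
| HbA1c, FPG (Table 5); weight, vital signs (Table 1) | weeks 0, 1, 4, 8, 12, 16, 20, 24 | at least 1 once a post-baseline visit has taken place |

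Section 3.1 allows up-titration on site FPG at Visit 3 (week 1) and every later visit, or on diary glucose. For the first two rows, the share of patients up-titrated before Visit 9 who have no eligible value is therefore 100%. A patient first up-titrated at Visit 9 keeps the week-24 value.

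**2. Does another rule rescue them?** Carrying the last observation forward needs an observation. Baseline carry-forward is not stated. The patient remains in the full analysis set through other variables but has no change score for these six. The one supportive analysis in 6.4.1 that ignores the up-titration cut is for HbA1c.

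**3. Later time points.** If the same rule is used at weeks 48 and 104, every later lipid or waist value of such a patient also follows the first up-titration. The patient is missing there too. Someone first up-titrated after Visit 9 at least keeps the week-24 value.

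**4. Denominator.** The plan's figure (6.5) is 153 evaluable per arm for a difference of 0.5, SD 1.2, two-sided level 0.019 and 90% power. The normal approximation gives n = 2 × (2.3455 + 1.2816)² × 1.2² / 0.5² = 151.6, so 152. The noncentral t gives 153 (power 0.9001). Then 153 / 0.95 = 161.05, planned as 161, and 4 × 161 = 644. The sample size reproduces and is not in question. Section 6.5 also reports 808 actually randomised, or 808 / 4 = 202 per arm on average.

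**5. Size of the loss.** Patients lost per arm = N × u, where u is the proportion up-titrated before Visit 9. The documents give no u, so the values below are assumptions.

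| Assumed u | Lost of 161 | Lost of 202 |
|---|---|---|
| 5% | 8 | 10 |
| 10% | 16 | 20 |
| 20% | 32 | 40 |
| 30% | 48 | 61 |

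If u differs by arm, so does the loss. With an assumed 20% on placebo and 5% on active, 32 and 8 of 161 are removed.

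**6. Direction of bias.** In one arm, let d be the mean change of up-titrated patients minus that of the rest. The mean over all patients exceeds the mean over retained patients by u × d. For active minus placebo, the all-patient difference and the retained-patient difference are therefore apart by u(active) × d(active) − u(placebo) × d(placebo). The documents give none of the four quantities. The gap is zero if d is zero in both arms, and it changes sign if d does.

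**The case against.** The strongest reply is that 6.4.1 makes a deliberate choice of estimand: the effect without added insulin. Section 1.2 names weight gain as a common problem of insulin therapy, so a value taken after up-titration mixes the study drug with extra insulin. For body weight and blood pressure this stands. Both are measured at every site visit, so the rule normally has a value to use. It does not rescue lipids, FFA and waist: with no measurement before up-titration, the rule cannot estimate that effect for these patients and simply omits them.

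A reader might infer that 3.1 restricts the carry-forward to HbA1c and FPG and so contradicts 6.4.1. The text does not go that far. It names two variables without excluding others, and both statements can be followed at once. This is a difference in scope to align.

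A reader might also infer that the omission biases lipid differences towards no effect because placebo would lose more patients with worse values. The documents support neither the imbalance nor its sign. Up-titrated patients might have worse, equal or better lipids at week 24 after more insulin.

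The number affected may be small. In the first 24 weeks the triggers are fasting glucose above 240 and later 220 mg/dl, site values need confirmation, and patients are told to keep insulin unchanged. That limits the size but does not remove the defect.

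Finally, the SAP might say what happens when no earlier value exists. Details of that kind do belong there. Here, however, the protocol already fixes a rule, and the rule excludes a collected value. The descriptive time-course summaries in 6.4.1 may show observed week-24 values, but they are not the between-arm comparison.

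**Conclusion.** The point holds for six other-secondary variables: TC, LDL-C, HDL-C, TG, FFA and waist. As written, 6.4.1 gives no analysable week-24 change for any patient up-titrated before Visit 9, and through 6.4.2 none at weeks 48 or 104. The schedule establishes this without assumptions. The number of patients does rest on an assumption: about 8 to 48 of 161 per arm for up-titration rates of 5% to 30%. The direction and size of any bias cannot be determined.

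The consequence is moderate. Section 6.2 treats other secondary variables as supportive, and they stand outside the hierarchical procedure, so no confirmatory conclusion depends on them. It should not be read as a flaw in the primary analysis or in the key secondary analysis of body weight. Censoring weight and blood pressure at up-titration may stay as a choice of estimand.

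**What to change.** Add one sentence to 6.4.1: for TC, LDL-C, HDL-C, TG, FFA and waist circumference, the observed week-24 value, or the early-termination value for a patient who stops before week 24, is used whether or not insulin was up-titrated. State the matching rule for weeks 48 and 104 in 6.4.2. Keep the analysis censored at up-titration as a sensitivity analysis for these variables, and report how many patients per arm it omits.

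Align the carry-forward wording in 3.1 and 4.7.4.1 with 6.4.1, so that all three state the same list of variables to which the cut applies. Make the change before the treatment codes are opened for the 24-week analysis. If they are already open, report the result as an additional analysis.

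The cost is a short text change and some programming. No new visits or samples are needed, because the values are already scheduled. The downside is that these six endpoints will then include any effect of added insulin, and the report should say so.

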- Change in seated systolic BP and seated diastolic BP from baseline to week 104, and from week 48 to week 104 in patients with baseline seated systolic BP > 140 mmHg
- Percent change in total cholesterol (TC), low density lipoprotein cholesterol (LDL-C), high density lipoprotein cholesterol (HDL-C), triglycerides (TG) and free fatty acids (FFA) from baseline to week 104, and from week 48 to week 104

Patient reported outcomes

(PROs) (not applicable)

Health economics (not applicable)

Pharmacokinetics

Plasma samples for analysis of dapagliflozin will be obtained at the Week 8 and Week 20 visits immediately prior to dosing, 60 minutes post-dose and 180 minutes post dose.

Genetics

Blood samples will be taken from patients who separately consent to optional blood sampling donation for deoxyribonucleic acid (DNA) analysis. The purpose is to enable future pharmacogenetic research studies. DNA collected from the samples and health information collected from the main clinical study may be used to investigate the effects of DNA variation on response to study treatments and the causes and further progression of type 2 diabetes and other metabolic diseases. Samples from this and other clinical studies may also be used in conjunction to accomplish these objectives. The samples will be destroyed after 15 years.

Statistical methods

The primary outcome variable, change from baseline to week 24 in HbA1c, will be analyzed by an analysis of covariance model (ANCOVA) which will be used to derive least squares estimates of the treatment differences (each dapagliflozin dose group versus placebo) in mean change with corresponding p-values and two-sided 95% confidence intervals. A hierarchical closed testing procedure will be used to control the Type I error rate across the primary and key secondary objectives. Efficacy will primarily be evaluated using the full analysis set.

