Patients with type 2 diabetes on at least 30 IU of insulin per day for at least 8 weeks prior to enrolment, with or without OADs with known HbA1c values $\geq 7,5\%$ and $\leq 10,5\%$ will provide informed consent and submit laboratory samples. Patients on metformin therapy should be on at least 1500 mg/day of metformin or at the maximum tolerable dose for a period of at least 8 weeks prior to enrolment. Patients on other OAD medications should be on at least half maximum daily recommended dose of the OAD for a period of at least 8 weeks prior to enrolment. Patient will be provided with a glucometer and a patient diary and be instructed to record their daily SMBG as well as insulin use during the next two weeks. Patients will be instructed to continue their current insulin and if applicable any ongoing OAD therapy at the same dose level during enrolment period.

24-week double-blind treatment period (Visit 2–9; week 0 to week 24)

If all lab inclusion criteria for V1 are met, Visit 2 should occur two weeks after visit 1. All further applicable inclusion and exclusion criteria will be checked and the mean daily insulin dose will be calculated by the investigator. The calculated mean daily insulin dose is an average total daily insulin dose used over the last seven documented days. Eligible patients with at least 30 IU calculated mean daily insulin dose will be randomized if the daily insulin requirements over the past seven days with insulin dose documentation does not vary more than 10% of the calculated mean daily insulin dose on more than one occasion. (For example for a patient whose calculated mean daily insulin dose is 50 IU, daily doses may not be <45 and >55 IU on more than one occasion within the past seven days with insulin dose documentation).

Eligible patients will be randomized in a 1:1:1:1 ratio to receive either dapagliflozin at 2.5 mg, 5 mg, 10 mg or placebo once daily. Patients will return for visits 1 week after start of treatment and then approximately every 4 weeks to assess efficacy and safety of the treatment. The patients will be instructed to record their fasting SMBG as well as insulin use daily. The patients will further be instructed to always self-monitor plasma glucose in case of symptoms suggestive of hypoglycaemia and to register any signs of hypoglycaemia in the supplied diary. During the study treatment the patients will be instructed to keep their insulin (and if applicable OAD) dose unchanged.

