6.2 Description of outcome variables in relation to objectives and hypotheses

The primary objective of the study is to assess the efficacy of 2.5 mg, 5 mg and 10 mg dapagliflozin compared to placebo as add-on therapy to insulin in improving glycaemic control in subjects with type 2 diabetes who have inadequate glycaemic control on ≥ 30 IU injectable insulin daily for at least 8 weeks prior to enrolment, as determined by the change in HbA1c levels from baseline to week 24. The objective will be statistically analyzed using Dunnett's method (overall type I error rate for the primary endpoint 0.05). The significance level for each pair-wise group comparison of dapagliflozin versus placebo will be approximately 0.019.

Key secondary objectives are to compare the effects of each dose of dapagliflozin versus placebo given as add-on therapy to insulin after a 24-week double-blind treatment period by evaluation of:

1. The change in body weight from baseline to week 24
2. The absolute change in calculated mean daily insulin dose from baseline to week 24
3. The proportion of subjects with calculated mean daily insulin dose reduction from baseline to week 24

4. The change in FPG from baseline to week 24

The statistical testing of the primary and key secondary outcome variables will proceed in a sequential manner, to control the type I error rate within each dapagliflozin group at the 0.05 level. Specifically, the significance or non-significance of the treatment comparisons for the primary outcome variable will determine which, if any, statistical inferences are made for the key secondary outcome variables. Only those dapagliflozin groups significantly superior to placebo for the primary outcome variable will have statistical inference versus placebo for the first key secondary outcome variable, (1). Then, the testing for the other key secondary outcome variables will proceed so that

- the significance or non-significance of the treatment comparisons for (1) will determine which, if any, statistical inferences are made in treatment comparisons for (2), and
- the significance or non-significance of the treatment comparisons for (2) will determine which, if any, statistical inferences are made in treatment comparisons for (3), and
- the significance or non-significance of the treatment comparisons for (3) will determine which, if any, statistical inferences are made in treatment comparisons for (4).

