If at least one of the primary comparisons between a dapagliflozin treatment group and the placebo treatment group is significant at the 0.019 level for the primary outcome variable, all statistical tests for the four key secondary outcome variables will be performed and nominal p-values will be reported. However, in order to protect the global type I error rate of the hierarchical testing procedure, the interpretation of the statistical significance of treatment comparisons for each secondary outcome variable will be done using a step-wise procedure.

Other secondary outcome variables shall provide supportive efficacy and safety information regarding the differences between the treatment groups.

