6.5 Determination of sample size

Each pairwise treatment group comparison will be tested at a significance level of approximately 0.019, according to Dunnett's method, in order to maintain an overall type I error rate < 0.050 for the primary objective. To detect a difference of 0.5% between each dapagliflozin group versus placebo for changes from baseline to week 24 in HbA1c, assuming a SD = 1.2%, and at a two-sided significance level of 0.019, 153 evaluable subjects are needed in each treatment group to provide 90% power. Assuming that 5% of the subjects will not be evaluable in the full analysis set, 161 subjects per treatment group (644 subjects total) are planned for randomization.

Approximately 700 patients will be offered to enter the long-term extension period II. This estimate is based on the number of actually randomised patients (808) and the assumption that approximately 14 % of the randomised patients will have been withdrawn at week 48 (visit 12).

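### The three primary HbA1c contrasts are tested at about 0.019 each but reported with ordinary 95% intervals; adding Dunnett simultaneous intervals would align the two at little cost

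*Protocol*

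**What the plan says.** Section 6.2 sets Dunnett's method for the primary objective, with "overall type I error rate for the primary endpoint 0.05", and adds: "The significance level for each pair-wise group comparison of dapagliflozin versus placebo will be approximately 0.019". The same section applies that threshold when it makes the key secondary tests conditional on at least one primary comparison that "is significant at the 0.019 level for the primary outcome variable". Section 6.5 sizes the trial at the same level.

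Section 6.4.1 defines the contrasts as "pair-wise treatment group comparisons: each dapagliflozin treatment group versus placebo". From the ANCOVA it reports the difference for each dose "in mean change with corresponding p-value and two-sided 95% confidence interval". The statistical methods part of the synopsis says the same: "in mean change with corresponding p-values and two-sided 95% confidence intervals".

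No section gives a simultaneous, Dunnett-adjusted or 98.1% interval for these contrasts. The word nominal is used for key secondary p-values in section 6.2 and for secondary p-values in section 6.4.1, but not for the primary interval.

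**The concern.** The level of the test and the level of the interval differ for the same three contrasts. The p-value is compared with 0.019, so it is a per-comparison p-value, and the interval paired with it comes straight from the ANCOVA at 95%. That an unadjusted interval is meant is a reading, since the protocol does not use the word, but it is the natural one.

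If a dose gives a p-value between 0.019 and 0.05, the report will say that superiority was not shown and print an interval lying wholly on one side of zero. Under section 6.2 that dose is also barred from inference on all four key secondary endpoints. A reader who looks first at the estimate and its interval could take the wrong message about that dose from the confirmatory part of the study.

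**Working it through.** **Inputs.** Three contrasts share one placebo arm. Section 3.1 states: "Eligible patients will be randomized in a 1:1:1:1 ratio to receive either dapagliflozin at 2.5 mg, 5 mg, 10 mg or placebo once daily". Equal arms give a correlation of 0.5 between the contrasts. Section 6.5 gives the design effect ("To detect a difference of 0.5% between each dapagliflozin group versus placebo"), SD 1.2, two-sided level 0.019, 90% power, 153 evaluable per arm, 5% not evaluable, 161 per arm (644 in total), and 808 patients actually randomised.

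**The plan's own figures.**
- Sample size: the noncentral t calculation at two-sided 0.019 gives power 0.9001 at 153 per arm. The figure of 153 reproduces.
- Randomised number: 153 / 0.95 = 161.05, which the plan takes as 161; 4 × 161 = 644.
- Dunnett level: with 4 × 153 − 6 = 606 degrees of freedom, the two-sided critical value for three contrasts at overall 0.05 is 2.355. This is a per-comparison level of 0.0188, in line with the stated approximate 0.019.

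**Joint coverage of three ordinary 95% intervals.** For correlation 0.5 and critical value c, the normal-limit probability that all three intervals cover is

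∫ φ(x) [Φ(x + √2·c) − Φ(x − √2·c)]³ dx.

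At c = 1.96 this is 0.8746. The multivariate t version with 606 degrees of freedom gives 0.8747, and it is 0.875 to three decimals at 161 and 202 per arm as well. Three independent intervals would give 0.95³ = 0.857.

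**Where test and interval part.** SE = 1.2 × √(2/153) = 0.1372. The 95% interval excludes zero from an observed difference of 1.96 × 0.1372 = 0.269. The test at 0.019 (z = 2.3455) rejects from 2.3455 × 0.1372 = 0.322. Observed differences between about 0.27 and 0.32 points fall in the gap.

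**How often, per dose.** The chance is Φ(δ/SE − 1.96) − Φ(δ/SE − 2.3455) for a true difference δ in favour of dapagliflozin. The 808 randomised give 808 / 4 = 202 per arm if the arms are equal, and 202 × 0.95 = 191.9, about 192, if 5% are not evaluable.

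| True difference | 153 per arm (SE 0.1372) | 192 per arm (SE 0.1225) | 202 per arm (SE 0.1194) |
|---|---|---|---|
| 0.5 (design) | 0.954 − 0.903 = 5.1% | 0.983 − 0.959 = 2.4% | 0.987 − 0.967 = 2.0% |
| 0.4 (assumed) | 11.5% | 8.3% | 7.5% |
| 0.3 (assumed) | 0.590 − 0.437 = 15.3% | 14.6% | 14.3% |
| 0.2 (assumed) | 12.0% | 13.4% | 13.7% |

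**Width after the change.** The ratio of critical values is 2.355 / 1.964 = 1.20. Half-widths at 153 per arm are 2.355 × 0.1372 = 0.323 against 1.964 × 0.1372 = 0.269 points. At 202 per arm they are about 0.281 against 0.234.

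**The case against.** The strongest reply is that the protocol contains no conflict in its decision rule. Sections 6.2 and 6.5 decide by the test at about 0.019, and section 6.4.1 refers the interpretation of significance back to section 6.2. Nowhere does an interval decide superiority. This stands. A reader might infer that the intervals contradict the formal conclusion, or that they let a dose succeed at 0.05, but the text supports neither.

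A second reply is that joint coverage is never promised. The protocol claims control of the type I error of the tests and a 95% interval for each difference, and each interval has that coverage. This also stands. The 87.5% describes what the three intervals do together and refutes no statement in the document. Marginal intervals beside multiplicity-controlled tests are a legitimate choice when labelled as such.

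Third, labelling or adding intervals could be left to the SAP, which was not available and may do so. This stands only in part. The point is not that the protocol is silent: it states both levels for the same contrasts, and an SAP that follows section 6.4.1 to the letter would carry the mismatch forward.

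Fourth, the planned 153 per arm overstates the frequency at the design effect, because 808 patients were randomised. That is correct, and the table shows the fall from about 5% to about 2%. At an assumed difference of 0.3 the larger sample makes little difference.

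**Conclusion.** The point holds as a cheap improvement in reporting. The interval level stated for the confirmatory result does not match its test level, so a dose with a p-value between 0.019 and 0.05 would fail while its interval excludes zero. With SD 1.2, the chance per dose is about 5% at the design difference of 0.5 and the planned 153 per arm, about 2% at 192 to 202 per arm, and about 15% at a difference of 0.3. Differences below 0.5 are assumptions, not figures from the protocol. The larger arm sizes assume equal allocation of the 808, and the 192 also assumes the 5% non-evaluable rate.

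It would go too far to conclude that the primary analysis is invalid, that its type I error is inflated by these intervals, or that the trial is too small. The Dunnett level and the 153 per arm both reproduce, and none of the confirmatory decisions would change.

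**What to change.** In section 6.4.1 and in the statistical methods of the synopsis, name Dunnett simultaneous 95% intervals (about 98.1% individually) and Dunnett-adjusted p-values as the confirmatory result for the three primary contrasts. The adjusted p-values are compared with 0.05 and the unadjusted ones with the per-comparison level of about 0.019, so say which is shown. Keep the ordinary 95% intervals beside them, labelled nominal and not deciding significance. If simultaneous intervals are not wanted, a sentence giving that label is the least that is needed.

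The cost is wording in the protocol and the SAP, with no new data or patients. The one drawback is a confirmatory interval about 20% wider: a half-width of about 0.32 instead of 0.27 points at 153 per arm.
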